8.5.2 Criteria for suspension/dose reduction of TAS-102

The criteria for suspension/dose reduction and doses of TAS-102 are shown in Tables 8.h-j.

CONFIDENTIAL

Table 8.h Criteria for suspension of TAS-102

Item	Suspension criteria
Hemoglobin concentration	< 7.0 g/dL
Neutrophil count	< $1.0 \times 10^3/\Lambda$
Platelet count	< $5.0 \times 10^4/\Lambda$
Total bilirubin	> 2.0 mg/dL
AST	> 100 U/L
ALT	(> 200 U/L with liver metastasis)
Serum creatinine	> 1.5 mg/dL
Peripheral sensory neuropathy	Grade 3 or higher
Other non-hematologic toxicity	Grade 3 or higher

Dose suspension is allowed as necessary at the discretion of the investigator or the subinvestigator due to adverse events not listed above.

If adverse events meeting the criteria for dose reduction of TAS-102 shown in Table 8.i occur during the previous course (including the suspension period), dose will be reduced in course units, with a daily dose unit of reduction of $10 \text{ mg/m}^2/\text{day}$, when TAS-102 is resumed. However, the minimum dose will be $40 \text{ mg/m}^2/\text{day}$ (Table 8.j).

Table 8.i Criteria for dose reduction of TAS-102

Item	Criteria for dose reduction
Neutrophil count	< $0.5 \times 10^3/\Lambda$
Platelet count	< $5.0 \times 10^4/\Lambda$

Dose reduction is allowed as necessary at the discretion of the investigator or the subinvestigator due to adverse events not listed above.

Table 8.j Doses of TAS-102

Dose reduction level	TAS-102
Initial dose	35 mg/m^2 ($70 \text{ mg/m}^2/\text{day}$)
-1	30 mg/m^2 ($60 \text{ mg/m}^2/\text{day}$)
-2	25 mg/m^2 ($50 \text{ mg/m}^2/\text{day}$)
-3	20 mg/m^2 ($40 \text{ mg/m}^2/\text{day}$)
-4	Discontinuation (no resumption)

When the subject meets the criteria for suspension of TAS-102, administration of TAS-102 will be suspended, and only panitumumab therapy will be administered. For the next dose of TAS-102,

CONFIDENTIAL

TAS-102 treatment will be resumed after it is confirmed that the subject meets the criteria for initiation of TAS-102 treatment (however, when the subject satisfies the criteria for initiation of treatment from Day 13 to Day 28 of the suspension period, treatment will be resumed on Day 29). However, if TAS-102 cannot be administered for more than 28 days from the scheduled day of initiation of treatment, treatment with TAS-102 will be discontinued. (At this time, the day of initiating panitumumab monotherapy after it is determined that treatment with TAS-102 will be discontinued will be defined as the day for starting the course (Day 1), and the course will be defined as the administration of panitumumab between Day 1 and Day 28 on Days 1 and 15.)

8.6 Criteria for dose increase of protocol treatment

The dose should not be increased after dose reduction for any of the drugs.

8.7 Criteria for discontinuation of protocol treatment for each subject

The number of doses is not specified. However, protocol treatment should be discontinued when any of the criteria for discontinuation of protocol treatment listed below is met. The date of discontinuation of protocol treatment is defined as the date when the investigator or the subinvestigator decides on discontinuation of protocol treatment. The investigator or the subinvestigator should record the main reason for discontinuation of protocol treatment in the case report form (hereinafter referred to as CRF) according to the classification described below. For subjects discontinuing before enrollment, see 9.3 Records of subjects who discontinued before enrollment.

1. Lack of efficacy (exacerbation)

When PD is evident in the clinical or imaging evaluation

2. Adverse event

Discontinuation of treatment due to an adverse event in the opinion of the investigator or the subinvestigator, or according to the protocol treatment discontinuation criteria. However, death during protocol treatment will be classified in “4. Death during protocol treatment” and not in this item.

Protocol treatment is postponed due to adverse event for 58 days or more after the day of starting the last course. However, postponement due to holidays is allowed.

3. Voluntary discontinuation

A subject wishes to discontinue study participation. The reason for discontinuation should be recorded in CRF when it is clarified.

CONFIDENTIAL

Note: Attempts should be made as best as possible to clarify the reason for voluntary discontinuation. (Discontinuation due to adverse event or lack of efficacy should not be classified as “voluntary discontinuation”).

4. Death during protocol treatment

Death before discontinuation of protocol treatment is decided. Date of death, reason of death (protocol treatment related, primary disease, others) should be described in the CRF.

5. Significant deviation from the protocol

When study continuation may cause intolerable risk to the health of a subject because the subject was found not to satisfy the inclusion criteria specified in the protocol after enrollment or the protocol has not been observed.

6. Lost to follow-up

When subject fails to make visits and cannot be contacted. The attempts that were made to contact the subject should be recorded in the source documents.

7. Discontinuation of the entire study

For example, when the sponsor decides to discontinue the clinical study upon the recommendation of the DMC. See 6.3.1 Criteria for discontinuation of entire clinical study for details.

8. Pregnancy

When a female subject is found to be pregnant.

Note: Study participation should be immediately discontinued when pregnancy is known. See “9.2.13 Pregnancy” for procedures.

9. Others

When the investigator or the subinvestigator decides that protocol treatment should be discontinued for other reasons. Details should be described in the CRF.

8.8 Procedures for Discontinuation or Withdrawal of a Subject

The investigator or the subinvestigator may discontinue a subject's study participation at any time during the study when the subject meets the study termination criteria described in Section 8.7. In addition, a subject may discontinue his or her participation without giving a reason at any time during the study. Should a subject's participation be discontinued, the primary reason for termination must be recorded in the CRF by the investigator or the subinvestigator. In addition, efforts should be made to perform all tests/observations/evaluation scheduled at the time of discontinuation.

8.9 DLT

In this study, DLT will be assessed based on the toxicity in 6 subjects at maximum enrolled in phase I part. The sponsor will confirm the opinion of the DMC in a suitable manner when evaluating DLT.

8.9.1 DLT Evaluation Period

The DLT evaluation period will be the period from Day 1 of Course 1 of protocol treatment to Day 1 of Course 2. However, it is mandatory that the treatment initiation criteria for both panitumumab and TAS-102 be satisfied in order to start Course 2 of protocol treatment. Furthermore, the DLT evaluation period will be the period until the test day at discontinuation of protocol treatment for subjects who could not start Course 2 of protocol treatment until Day 57 due to adverse events and discontinued the protocol treatment.

8.9.2 Subjects Included in the DLT Evaluation

Subjects enrolled in the phase I part of the study will be included in the DLT evaluation. Subjects will be excluded from the DLT evaluation if at least the designated dose of protocol treatment is not administered by the end of Course 1 (except when the protocol treatment is discontinued due to DLT), if there are major protocol deviations such as the use of contraindicated drugs, or if the subject is determined to be unsuitable for the DLT evaluation. The designated dose is 75% (15 doses) of the total number of doses (20 doses) of panitumumab (2 doses of 6 mg/kg) and TAS-102 (2 doses daily of 35 mg/m²) on Days 1-5 and Days 8-12.

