6.0 CLINICAL STUDY DESIGN

6.1 Clinical study design

This phase I/II study is a multi-center, open-label single-arm study that consists of a phase I part (dose de-escalation) which will assess the tolerability and RD of Panitumumab in combination with TAS-102 as primary objective, and a phase II part which will assess the efficacy and safety of Panitumumab in combination with TAS-102 as primary objective in patients with RAS wild-type unresectable, advanced/recurrent colorectal cancer. In the phase I part, the subjects will be included sequentially into Cohort 1 and 2, 3 subjects each with the same dosage and administration. In the phase II part, 46 subjects will be included additionally for RD confirmed in the phase I part.

[figure not shown]

Figure 6.a Outline of study design

In the phase I part, each cohort will be conducted with 3 subjects, the sponsor will assess tolerability of the dosage and administration based on the incidence of Dose Limiting Toxicity (hereinafter referred to as DLT) during the assessment period and determine whether or not to move on to the next cohort (opinion from the Data Monitoring Committee [hereinafter referred to as DMC] will be confirmed appropriately upon determination). Therefore, in Cohort 1, if occurrence of DLT is ≤ 2 subjects out of 3, the dosage and administration will be determined tolerable and will move on to Cohort 2. However, if DLT is observed in 2 subjects during DLT assessment period in Cohort 1, subjects will be included one at a time in Cohort 2 in consideration for safety to assess DLT.

CONFIDENTIAL

Similarly 3 subjects will be included in Cohort 2 and DLT will be assessed in a total of 6 subjects of Cohort 1 and 2 at most. If DLT is observed in 3 subjects included in Cohort 1, or DLT is observed in 3 subjects from a total of 6 subjects of Cohort 1 and 2, the sponsor will promptly request to postpone new enrollment of subjects to each site and after consultation with the Research Steering Committee and DMC on the continuation of the study, will determine whether or not to continue the study.

If study is to be continued, taking in account of the adverse event that occurred, either panitumumab or TAS-102 or both drugs will be reduced one step and re-conducting the phase I part similarly will be considered. If DLT is observed in 3 subjects after reducing 1 step of panitumumab or TAS-102 or both drugs, the study will be discontinued.

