8.1 Definition of protocol treatment

With protocol treatment in principle, combination therapy with panitumumab and TAS-102 stipulated in the “8.2 treatment regimen” will be conducted, and even if any of the criteria for suspension or discontinuation of each drug is met, treatment with other drugs will be continued unless any of the criteria for discontinuation of protocol treatment is met (such as in case of PD).

Protocol treatment in principle will be initiated within 14 days of entry.

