8.3 Recommended dose of protocol treatment

The dose will be calculated based on the body surface area (calculated using the DuBois & DuBois formula) and body weight at the time of study entry. Dose for panitumumab is round down in unit of 10 mg for reference, TAS-102 will be as Table 8.b and 8.c. At the time of entry, the data center will announce the reference dose and this should be recalculated and confirmed at the study site. The dose should be recalculated for 10% change in body weight, in principle, but at the discretion of the investigator or the subinvestigator. If more than 10% change in body weight is observed further after the recalculation the same method should be taken. However, TAS-102 dosage will be adjusted by course and adjustment from the middle of the course will not be conducted. Even if suspended during treatment period, drug will not be re-taken and drug will be taken according to stipulated treatment schedule (after 1 to 5 days, 8 to 12 days from initial administration of each course). Also, if subject missed any dose, remaining drug should not be taken.

Table 8.b TAS-102 dosage

TAS-102 dosage (twice daily)	Body surface area (m ²)	One dose (mg)	Dose per day (mg)	One dosage	
				15 mg tablet	20 mg tablet
35 mg/m ² (70 mg/m ² /day)	< 1.07	35	70	1	1
	1.07 – 1.22	40	80	0	2
	1.23 – 1.37	45	90	3	0
	1.38 – 1.52	50	100	2	1
	1.53 – 1.68	55	110	1	2
	1.69 – 1.83	60	120	0	3
	1.84 – 1.98	65	130	3	1
	1.99 – 2.14	70	140	2	2
	2.15	75	150	1	3

Table 8.c TAS-102 dosage when dose is adjusted

TAS-102 dosage (twice daily)	Body surface area (m ²)	One dose (mg)	Dose per day (mg)	One dosage	
				15 mg tablet	20 mg tablet
Drug reduction (35 mg/m² to 30 mg/m²)					
30 mg/m² (60 mg/m²/day)	< 1.09	30	60	2	0
	1.09 – 1.24	35	70	1	1
	1.25 – 1.39	40	80	0	2
	1.40 – 1.54	45	90	3	0
	1.55 – 1.69	50	100	2	1
	1.70 – 1.94	55	110	1	2
	1.95 – 2.09	60	120	0	3
	2.10 – 2.28	65	130	3	1
	2.29	70	140	2	2
	Drug reduction (30 mg/m² to 25 mg/m²)				
25 mg/m² (50 mg/m²/day)	< 1.10	25	50	2 (after dinner)	1 (after breakfast)
	1.10 – 1.29	30	60	2	0
	1.30 – 1.49	35	70	1	1
	1.50 – 1.69	40	80	0	2
	1.70 – 1.89	45	90	3	0
	1.90 – 2.09	50	100	2	1
	2.10 – 2.29	55	110	1	2
	2.30	60	120	0	3
Drug reduction (25 mg/m² to 20 mg/m²)					
20 mg/m² (40 mg/m²/day)	< 1.14	20	40	0	1
	1.14 – 1.34	25	50	2 (after dinner)	1 (after breakfast)
	1.35 – 1.59	30	60	2	0
	1.60 – 1.94	35	70	1	1
	1.95 – 2.09	40	80	0	2
	2.10 – 2.34	45	90	3	0
	2.35	50	100	2	1

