8.10 Replacement/Addition of Subjects

Should there be, during the DLT evaluation period in the phase I part of the study, a major deviation from the protocol affecting the DLT evaluation for a reason other than an adverse event classified as a DLT or if DLT cannot be evaluated appropriately, that subject can be excluded from the DLT evaluation and a new subject can be enrolled and added to that cohort.

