10.1.8 Action taken for protocol treatment

As for action concerning protocol treatment, when protocol treatment is discontinued as an action against the concerned adverse event, it will be defined as “discontinuation”.

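### The DLT evaluation set can drop a subject who has a DLT, because the minimum-dose rule exempts only discontinuation of protocol treatment and not suspension of a drug

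*Protocol*

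**What the plan says.** Protocol 8.9.2 starts from all subjects enrolled in phase I and then excludes, in mandatory wording, anyone who has not received the designated dose by the end of Course 1. The designated dose is 15 of 20 doses (75%). The only exception to this dose ground is "except when the protocol treatment is discontinued due to DLT". SAP v4.0 section 6.1 reproduces the rule with the same exception.

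Other sections treat suspension of a drug as something different from discontinuing protocol treatment:

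- Protocol 8.1: "even if any of the criteria for suspension or discontinuation of each drug is met, treatment with other drugs will be continued", unless a criterion for stopping protocol treatment as a whole is met.
- Protocol 8.5.2, for a subject who meets the TAS-102 suspension criteria: "administration of TAS-102 will be suspended, and only panitumumab therapy will be administered". If the subject meets the initiation criteria again "from Day 13 to Day 28 of the suspension period, treatment will be resumed on Day 29".
- Protocol 8.3: "Even if suspended during treatment period, drug will not be re-taken", so doses lost to a suspension stay lost.
- Protocol 10.1.8 records the action as a discontinuation "when protocol treatment is discontinued as an action against the concerned adverse event".

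Protocol 13.2.3.1 evaluates DLT incidence in the DLT evaluation set according to the 6.1 design. SAP 6.3.1 takes both the DLT count and the denominator from that set. Under 6.1 new enrollment is put on hold if all three Cohort 1 subjects have a DLT, or if "DLT is observed in 3 subjects from a total of 6 subjects of Cohort 1 and 2". Two or fewer in six opens the route to phase II.

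**The concern.** A minimum-dose rule for DLT evaluability is meant to remove subjects who were too lightly exposed for the absence of a DLT to be informative. A subject who has already had a DLT is informative at any exposure. The exception in 8.9.2 recognises this only when protocol treatment is stopped. A DLT that leads to suspension, lost doses and a Day 29 restart is not covered.

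The error runs one way: removing a DLT can only lower the count. The count concerned is the phase I primary endpoint, and it feeds both the hold and the move to phase II.

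**Working it through.** **1. The plan's own figure.** TAS-102: 2 doses a day × (5 + 5) days = 20 doses; 0.75 × 20 = 15. The stated 15 is reproduced. A subject with 14 or fewer doses, that is more than 5 missed, falls below the minimum. The sentence names panitumumab as well as TAS-102, but 20 is the TAS-102 count alone; with the two panitumumab doses the total is 22 and 75% of it is 16.5. How panitumumab doses count is therefore unclear. This is a side point.

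**2. Who can be lost.** In phase I, TAS-102 starts after dinner on Day 1 (Table 8a footnotes). Cumulative doses: 5 by Day 3 dinner, 10 by Day 6 breakfast, 11 at Day 8 dinner, 15 at Day 10 dinner, 20 at Day 13 breakfast.

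- Suspended at the Day 8 visit with 10 taken: restarting at Day 11 breakfast leaves 1 + 1 on Day 11, 2 on Day 12 and 1 on Day 13, so 10 + 5 = 15 and the subject stays in. Restarting at Day 11 dinner gives 10 + 4 = 14, and the subject is out.
- Suspended at Day 8 with the second block missed and a restart on Day 29: 10 of 20 (50%), out.
- Suspended after Day 3 dinner with week 2 complete: 5 + 10 = 15, in.

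**3. Whether such a subject can have a DLT and stay on treatment.** Grade 3 or higher non-hematologic toxicity is a TAS-102 suspension criterion (Table 8.h). If clinically problematic and not exempted, it is also a DLT (8.9.3, item 5). Section 8.7 does not list a DLT as such among the reasons to discontinue. The combination is possible under the protocol as written.

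**4. Effect on the count.** Three DLTs in six subjects meets the hold. With one of them dropped the set shows 2/5, or 2/6 if a replacement without a DLT is enrolled.

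**5. Illustration.** Let p be the true DLT rate and q the share of DLT subjects dropped. The documents give neither, so both are assumed. With X ~ Bin(6, π),

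P(X ≤ 2) = Σ(k = 0 to 2) C(6,k) π^k (1 − π)^(6−k).

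- Nobody dropped: π = p. At p = 0.50: (1 + 6 + 15)/64 = 0.344.
- Dropped, not replaced: π = p(1 − q). At p = 0.50, q = 0.25: π = 0.375.
- Dropped and replaced until six are evaluable: π = p(1 − q)/(1 − pq). At p = 0.50, q = 0.25: π = 0.375/0.875 = 0.429.

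Chance of counting at most two DLTs (not replaced / replaced):

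| p | none dropped | q = 10% | q = 25% | q = 50% |
|---|---|---|---|---|
| 0.20 | 0.901 | 0.924 / 0.920 | 0.953 / 0.946 | 0.984 / 0.979 |
| 0.30 | 0.744 | 0.798 / 0.783 | 0.868 / 0.841 | 0.953 / 0.928 |
| 0.40 | 0.544 | 0.627 / 0.596 | 0.744 / 0.680 | 0.901 / 0.831 |
| 0.50 | 0.344 | 0.442 / 0.394 | 0.596 / 0.485 | 0.831 / 0.680 |

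These are chances that the hold is not triggered. They are not chances of entering phase II.

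**The case against.** The literal gap is hard to dispute, so the case on the other side concerns its reach.

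- **Neither outcome leads cleanly to phase II.** Two DLTs in five subjects avoids the hold but does not meet the wording of two or fewer in six. Replacement is doubtful too: 8.10 allows it for a major deviation "for a reason other than an adverse event classified as a DLT", or where DLT cannot be evaluated properly. A suspension directed by the protocol is not a deviation, and an established DLT has been evaluated. This stands as a limit on the illustration. It does not repair the endpoint. Section 8.10 is permissive and does not override the mandatory dose ground in 8.9.2; if it shows an intent to keep DLT subjects, 8.9.2 does not carry it out.
- **The hold may not depend on the set.** Section 6.1 speaks of DLTs seen in subjects of the two cohorts, and 8.9 of those enrolled in phase I, so the sponsor could count the event anyway. But 13.2.3.1 ties the 6.1 evaluation to the DLT evaluation set. At best the documents are mixed.
- **The case is narrow.** At least six doses must be lost, a DLT criterion met and treatment continued. DLTs after the 15th dose, short suspensions and discontinued subjects are unaffected. At a true rate of 20% the effect is small. This stands. The definition in 10.1.8 is also only a recording category and is weaker support than 8.1 and 8.5.2.
- **Other reviews exist.** The sponsor and steering committee assess all phase I safety data and the DMC's opinion is obtained (6.1, 8.9, 11.2). SAP 6.3.3 also tabulates adverse events in all eligible treated phase I subjects. These may well catch the event, but they leave the reported DLT incidence as it is.

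**Conclusion.** The concern holds. As written, 8.9.2 and SAP 6.1 exclude a subject who has a DLT, receives fewer than 15 of 20 doses through suspension and does not discontinue protocol treatment. The phase I DLT incidence can then be too low, never too high, and a true 3 of 6 can appear as 2 of 5. How often this would happen is unknown: it rests on an assumed DLT rate and an assumed dropped share, and ranges from a few percentage points at a 20% rate to a large change at 50%. Moving to phase II is not automatic, so the firm consequence is a wrong primary endpoint; a missed hold is possible but depends on how 6.1 is applied. The point should be corrected. The wording of the 20 doses is a minor addition.

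**What to change.** In protocol 8.9.2 and SAP 6.1, replace the exception with a statement such as: *Any subject with a DLT in the evaluation period is included in the DLT evaluation set, whatever doses were received and whether treatment was suspended or discontinued; the 75% minimum applies only to subjects without a DLT.* Align 8.10 so that a subject with an established DLT is neither excluded nor replaced. State how the two panitumumab doses enter the count of 20.

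The text change is one sentence in two places plus the alignment of 8.10. It alters the analysis set only, and no dose or treatment rule. The price is a possibly less favourable observed DLT rate. Planned enrollment ended in March 2017 and SAP v4.0 dates from July 2018, so a change at that stage would redefine the phase I set late. It should be dated, and any subject whose inclusion it alters should be listed.

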8.9.3 DLT Criteria

DLT is defined as any adverse event for which a causal relationship with protocol treatment cannot be denied falling in the following categories. Adverse events will be graded according to the "Common Terminology Criteria for Adverse Events (CTCAE), ver. 4.03." Further, DLT will be assessed from Day 1 of course 1 of protocol treatment, and if DLT does not occur by Day 1 of course 2, it will be handled as no occurrence of DLT in the subject. Adverse events that can clearly be denied of causal relationship with the protocol treatment will not be considered DLT. If serious adverse event or unexpected adverse event occurs which causal relationship with the protocol treatment cannot be denied other than the following, it may be determined as to whether or not to handle it as DLT in consultation with the Investigator, the Research Steering Committee and the sponsor.

1. Persistent Grade 4 neutropenia for more than 7 days under maximum supportive therapy

CONFIDENTIAL

2. Febrile neutropenia
3. Blood platelet decreased of Grade 3 requiring platelet transfusion or blood platelet decreased of Grade 4
4. If start of second course is delayed for more than 14 days due to adverse event related to protocol treatment
5. Grade 3 or higher non-hematologic toxicity that is clinically problematic however the following will not be applicable as DLT.
 - Grade 3 gastrointestinal symptoms that can be controlled with supportive care (appropriate use of antiemetics, antidiarrheals, etc.)
 - Grade 3 or higher electrolyte abnormalities that are not deemed clinically problematic

